### **1.1 Study design**

[figure not shown]
This is a phase II, randomized, open-label study evaluating efficacy and safety of canakinumab or pembrolizumab monotherapy or in combination as neoadjuvant treatment.

Approximately 110 subjects were planned to be randomized in a 2:2:1 ratio to one of the treatment arms (Canakinumab alone, Canakinumab in combination with Pembrolizumab and Pembrolizumab alone). Subjects randomized will receive two doses of canakinumab (200mg s.c. Q3W) alone or in combination with pembrolizumab or two doses of pembrolizumab as single agent (200mg i.v. Q3W) ([Figure 1-1](#)). Randomization will be stratified by histology (squamous vs non-squamous). Subjects with adenosquamous histology can be stratified as squamous or non-squamous based on the predominant histology.

The primary endpoint is the MPR rate as assessed by the percentage of subjects with  $\leq 10\%$  residual viable cancer cells based on central review. Primary analysis will be performed after all subjects have had surgical resection or have discontinued study treatment earlier due to any reason.

No formal interim efficacy analysis is planned in this study.

**Figure 1-1 Study Design**

Stratification by histology (squamous vs non-squamous)

Primary endpoint- major pathological response

## 1.2 Study objectives, endpoints and estimands

**Table 1-1 Objectives and related endpoints**

Objective(s)	Endpoint(s)
Primary objective(s)	Endpoint(s) for primary objective(s)

 
To assess the MPR rate (<math>\leq 10\%</math> of residual viable tumor cells) at the time of surgery for all subjects randomized to canakinumab alone and in combination with pembrolizumab based on central review
 
	
 
MPR rate based on central review
 

Secondary objective(s)	Endpoint(s) for secondary objective(s)

 
To assess the prevalence and incidence of IG (ADA) of canakinumab and pembrolizumab
 
To assess ORR in randomized subjects treated with canakinumab or pembrolizumab as monotherapy and in combination (local review)
 
To assess the PK of canakinumab and pembrolizumab as monotherapy and in combination
 
To assess surgical feasibility rate in each treatment arm based on randomized subjects
 
To assess the MPR rate at the time of surgery in (a) all subjects randomized to pembrolizumab monotherapy arm based on central review, (b) all randomized subjects based on local review in each treatment arm, (c) to estimate the difference in MPR and posterior probability of the difference
 
	
 
ADA prevalence at baseline and ADA incidence on-treatment
 
Overall response rate based on local investigator assessment per RECIST 1.1
 
Concentrations of canakinumab, pembrolizumab
 
Surgical feasibility rate
 
(a) MPR based on central review (b) MPR based on local review (c) Difference in MPR rate based on central review
 

Objective(s)	Endpoint(s)

in MPR <math>\geq</math> 10% between subjects randomized to canakinumab + pembrolizumab combination and pembrolizumab alone based on central review.
 

• To evaluate safety and tolerability of canakinumab and pembrolizumab as monotherapy or in combination

• To assess the relationship between key blood or tissue based biomarkers and MPR

	

• Type, frequency and severity of AEs (Common Terminology Criteria for Adverse Events [CTCAE] v5.0), vital signs and laboratory abnormalities

• MPR based on the levels of biomarkers (PD-L1, CD8, hs-CRP, hs-IL-6) assessed at baseline and on treatment

### **1.2.1 Primary estimands**

The primary estimand will be described by the following five attributes:

1. The **target population** is defined as all randomized patients who are histologically confirmed NSCLC stage IB-IIIA (per AJCC 8th edition), deemed suitable for primary resection by treating surgeon, except for N2 and T4 tumors.
2. The **primary variable** is the percentage of subjects with a major pathological response (defined as  $\leq$  10% residual viable cancer cells per central review). Any patient who has  $>10\%$  residual viable cancer cells, or starts new antineoplastic therapy prior to surgery, or does not have the surgery performed, or have the surgery performed but with unevaluable MPR results, is considered as a non-responder.
3. The **study treatment** is canakinumab as monotherapy or in combination with pembrolizumab.

4. The **intercurrent events** of interest in this study are: start of new antineoplastic therapy prior to surgery and discontinuation of study treatment prior to surgery. These intercurrent events will be addressed as follows:
  - a. **Start of new antineoplastic therapy prior to surgery:** subject will be considered as non-responder (composite strategy)
  - b. **Discontinuation of study treatment prior to surgery:** subject will be included in the analysis regardless of this intercurrent event (treatment-policy strategy).
5. The **summary measure** is MPR rate with its corresponding two-sided exact binomial 95% confidence interval ([Clopper CJ and Pearson ES \(1934\). The use of confidence or fiducial limits illustrated in the case of the binomial. Biometrical, 26, 404-413.](#)) in canakinumab alone arm and canakinumab in combination with pembrolizumab arm.

## **2 Statistical methods**

### **2.1 Data analysis general information**

The final analysis will be performed by Novartis statistics and programming team. SAS version 9.4 or later will be used to perform all data analyses and to generate tables, figures and listings.

#### **2.1.1 Data included in the analysis**

Data from all participants who signed main informed consent in centers that participate in this study will be used in the analysis. Data collected after patients' withdrawal of informed consent for further participation in the study will not be reported (except for death date, if it is obtained from public records).

The analysis cut-off date for the primary analysis of study data will be established after all subjects have had surgical resection or have discontinued study treatment earlier due to any reason. All statistical analyses will be performed using all data collected in the database up to the data cutoff date. All data with an assessment date or event start date (e.g. vital sign assessment date or start date of an adverse event) prior to or on the cut-off date will be included in the analysis. Any data collected beyond the cut-off date will not be included in the analysis and will not be used for any derivations.

All events with start date before or on the cut-off date and end date after the cut-off date will be reported as 'ongoing'. The same rule will be applied to events starting before or on the cut-off date and not having documented end date. This approach applies, in particular, to adverse event and concomitant medication reports. For these events, the end date will not be imputed and therefore will not appear in the listings.

#### **2.1.2 General analysis conventions**

**Pooling of centers:** Unless specified otherwise, data from all study centers will be pooled for the analysis. Due to expected small number of subjects enrolled at centers, no center effect will be assessed.

**Qualitative data** (e.g., gender, race, etc.) will be summarized by means of contingency tables by treatment arm; a missing category will be included as applicable. Percentages will be calculated using the number of subjects in the relevant population or subgroup as the denominator.

**Quantitative data** (e.g., age, body weight, etc.) will be summarized by appropriate descriptive statistics (i.e. mean, standard deviation, median, percentiles, minimum, and maximum) by treatment arm.

### **2.1.3 General definitions**

#### **2.1.3.1 Study drug and study treatment**

The study drug refers to canakinumab and pembrolizumab. The study treatment refers to canakinumab monotherapy, canakinumab in combination with pembrolizumab, and pembrolizumab monotherapy.

#### **2.1.3.2 Date of first administration of study drug**

The date of first administration of study drug is defined as the first date when a non-zero dose of study drug is administered and recorded on the Dosage Administration Record (DAR) (e)CRF. The date of first administration of study drug will also be referred as *start date of study drug*.

Note : Dates from “DAR – PK sampling” (e)CRF will not be used for this derivation.

#### **2.1.3.3 Date of last administration of study drug**

The date of last administration of study drug is defined as the last date when a nonzero dose of study drug is administered and recorded on DAR (e)CRF. The date of last administration of investigational drug will also be referred as *end date of study drug*.

Note 1: Dates from “DAR – PK sampling” (e)CRF will not be used for this derivation.

Note 2: Last date of study drug exposure may not be the same as the last date of study drug (See [Section 2.1.3.6](#))

#### **2.1.3.4 Date of first administration of study treatment**

The date of first administration of study treatment is derived as the first date when a nonzero dose of any component of study treatment (canakinumab, pembrolizumab) was administered as per the DAR (e)CRF.

For the sake of simplicity, the date of first administration of study treatment will also be referred as *start date of study treatment*.

For canakinumab monotherapy and pembrolizumab monotherapy arms, the date of first administration of study treatment is the same as the date of first administration of study drug.

For canakinumab and pembrolizumab combination arm, the date of first administration of study treatment is derived as the first date when a nonzero dose of any component of study treatment was administered as per the DAR (e)CRF. For example: if 1st dose of canakinumab is

administered on 03-Jan-2019, and 1st dose of pembrolizumab is administered on 05-Jan-2019, then the date of first administration of study treatment is on 03-Jan-2019.

#### **2.1.3.5 Date of last administration of study treatment**

The date of last administration of study treatment is defined as the last date when a nonzero dose of study treatment (canakinumab, pembrolizumab) was administered as per DAR (e)CRF.

For canakinumab monotherapy and pembrolizumab monotherapy arms, the date of last administration of study treatment is the same as the date of last administration of study drug.

For canakinumab and pembrolizumab combination arm, the date of last administration of study treatment is derived as the last date when a nonzero dose of any component of study treatment was administered as per Dose Administration (e)CRF. For example: if the last canakinumab dose is administered on 15-Apr-2019, and the last dose of pembrolizumab is administered on 17-Apr-2019, then the date of last administration of study treatment is on 17-Apr-2019.

#### **2.1.3.6 Last date of exposure to study drug/treatment**

The study treatment schedule is organized in cycles of 21 days. The last date of exposure to study drug (canakinumab, pembrolizumab) will be derived as follows:

- Min ((last date of administration of study drug + (length of cycle duration - 1), i.e. [last date of study drug administration + 20]), date of death, last contact date in case subject is lost to follow-up, withdrawal of consent date)

The last date of exposure to canakinumab+pembrolizumab study treatment is derived to be the latest date among the last date of exposure to canakinumab and pembrolizumab. If the derived last date of exposure to study drug/study treatment goes beyond the data cutoff date, it should be truncated to the date of data cutoff. 'Date of last administration of study drug' and 'Date of last contact' are defined in [Section 2.1.3.3](#) and [Section 2.1.3.12](#) respectively.

#### **2.1.3.7 Study day**

The study day, describes the day of the event or assessment date, relative to the reference start date (randomization date or start date of study treatment).

The study day is defined as:

- The date of the event (visit date, onset date of an event, assessment date etc.) – reference start date + 1 if event is on or after the reference start date;
- The date of the event (visit date, onset date of an event, assessment date etc.) – reference start date if event precedes the reference start date.

The reference start date for safety assessments (e.g. adverse event onset, laboratory abnormality occurrence, vital sign measurement, dose interruption, PK and etc.) is the start date of study treatment.

The reference start date for all other non-safety assessments (e.g., MPR assessment, tumor response, and ECOG performance status) is the date of randomization.

The study day will be displayed in the data listings. If an event starts before the reference start date, the study day displayed on the listing will be negative.

### **2.1.3.8 Time unit**

A year length is defined as 365.25 days. A month length is 30.4375 days (365.25/12). If duration is reported in months, duration in days will be divided by 30.4375. If duration is reported in years, duration in days will be divided by 365.25.

### **2.1.3.9 Baseline**

For efficacy evaluations, the last non-missing assessment, including unscheduled assessments on or before the date of randomization is taken as “baseline” value or “baseline” assessment. In the context of baseline definition, the efficacy evaluations also include ECOG performance status. For biomarker, the last available data collected before the first dose of study treatment will be defined as “baseline”.

For safety evaluations, the last available assessment on or before the date of start of study treatment is taken as “baseline” assessment.

If subjects have no value as defined above, the baseline result will be missing.

In rare cases where multiple measurements meet the baseline definition, with no further flag or label that can identify the chronological order, then the following rule should be applied: If values are from central and local laboratories, the value from central assessment should be considered as baseline. If multiple values are from the same laboratory (local or central) or collected, then the worst value should be considered as baseline.

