6.6 Additional treatment guidance

6.6.1 Treatment compliance

Every time the study treatment is to be administered, IRT must be accessed to assign a medication (kit) number (for the investigational drug canakinumab) and/or registration of the other study drug (pembrolizumab) dispensed to the subjects.

The date and time of all study treatment administrations during the study and any deviations from the protocol treatment schedule will be captured on the appropriate drug accountability log.

Exposure to the study treatment will be based on the number of injections and/or infusions administered. Compliance with the study treatment will be assessed by the field monitor at each visit using vial counts and information provided by the pharmacist or by the investigator. All study treatment dispensed must be recorded in the drug accountability log.

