8.5 Additional assessments

8.5.1 Pharmacokinetics

8.5.1.1 Pharmacokinetics (PK), immunogenicity (IG) and pharmacodynamic (PD) assessments

To evaluate canakinumab and pembrolizumab exposure and immunogenicity in this indication, and also to evaluate exposure of the proposed dosing regimen, sample collections for analysis of PK and ADA are currently planned for canakinumab and pembrolizumab when administered alone and in combination.

Blood samples will be taken by either direct venipuncture or an indwelling cannula inserted in a forearm vein. Samples are collected from the arm opposite from infusion site. If drug was administered via a central venous catheter, sample collection for PK/IG/PD should be from a different site.

For all PK/IG/PD analytes, the exact date and time of dosing, as well as the exact collection date and time of blood sampling must be recorded on the appropriate eCRF. All samples will be given a unique sample number and a dose reference ID.

If subjects experience an AE or SAE leading to discontinuation of the study treatment, an unscheduled PK and IG blood sample should be obtained as close as possible to the event occurrence. If anaphylactoid reactions occur after injection, two more canakinumab IG samples (at the time of the event and 8 weeks later) need to be taken. Refer to [Central Laboratory Manual] and flowchart for detailed PK, IG and PD collection for canakinumab, and PK, IG collection for pembrolizumab.

Timepoints of blood sample collection for canakinumab PK, IG and PD are outlined in Table 8-5.

Table 8-5 Blood collection schedule for canakinumab (s.c. injection, 200 mg Q3W) PK, IG and PD

Dose Reference Identification (ID)	PK sample number	IG sample number ^b	Total IL-1 β (PD) sample number ^b	Scheduled timepoints (hours)		
				Cycle	Day	Scheduled time (hours)
101	1	11	21	1	1	0 h / pre-dose ^a
101/102*	2	12	22	2	1	504 h post dose / 0 h pre-dose ^a
	3	13	23	EOT	NA	Anytime

Dose Reference Identification (ID)	PK sample number	IG sample number ^b	Total IL-1 β (PD) sample number ^b	Scheduled timepoints (hours)		
				Cycle	Day	Scheduled time (hours)
	4	14	24	safety follow-up 1 (26 days post-EOT)	NA	Anytime
	5	15	25	safety follow-up 3 (78 days post-EOT)	NA	Anytime
	6	16	26	safety follow-up 5 (130 days post-EOT)	NA	Anytime
	1001+ ^c	2001+ ^d	3001+ ^e	NA	NA	Unscheduled

* The first Dose Reference ID is for last dose received prior to the collection of the PK sample, while the second Dose Reference ID is for the current dose

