12.5.2 Safety endpoints

For all safety analyses, the safety set will be used. All listings and tables will be presented by treatment group.

Safety summaries (tables, figures) include only data from the on-treatment period with the exception of baseline data which will also be summarized where appropriate (e.g. change from baseline summaries). In addition, a separate summary for death including on treatment and post treatment deaths will be provided. In particular, summary tables for AEs will summarize only on-treatment events, with a start date during the on-treatment period (treatment-emergent AEs).

The overall observation period will be divided into three mutually exclusive segments:

1. Pre-treatment period: from day of subject's informed consent to the day before first dose of study medication
2. On-treatment period: from day of first dose of study medication to 130 days after last dose of study medication
3. Post-treatment period: starting at day 131 after last dose of any component of the study treatment.

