### **2.1.3.10 On-treatment assessment/event and observation periods**

For adverse event reporting the overall observation period will be divided into three mutually exclusive segments:

1. ***pre-treatment period***: from day of subject’s informed consent to the day before first administration of study treatment
2. ***on-treatment period***: from date of first administration of study treatment to 130 days (approximately five terminal half-lives of canakinumab/pembrolizumab) after the date of last administration of study treatment
3. ***post-treatment period***: starting at day 131 after the date of last administration of study treatment

Safety summaries (tables, figures) and summaries of on-treatment death include only data from the on-treatment period with the exception of baseline data which will also be summarized where appropriate (e.g. change from baseline summaries). In addition, a separate summary for death including on treatment and post treatment deaths will be provided. In particular, summary tables for adverse events (AEs) will summarize only on-treatment events, with a start date during the on-treatment period (***treatment-emergent*** AEs).

An ***on-treatment assessment*** is defined as any assessment performed after the date of first administration of study treatment i.e. assessments performed in the following time interval (including the lower and upper limits): from date of first administration of study treatment +1 up to 130 days after the date of last administration of study treatment.

In case at time of the analysis, the date of last administration of study treatment is missing, on-treatment adverse event/assessment include any adverse event/assessment recorded in the database which occur after the start date of the study treatment.

However, all safety data (including those from the post-treatment period) will be listed and those collected during the pre-treatment and post-treatment period will be flagged.

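### The SAP sets safety baseline and the on-treatment assessment window by calendar date, so a value taken after the first dose on Day 1 can become the baseline and cannot count as an on-treatment assessment

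*SAP*

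**What the plan says.** SAP 2.1.3.9 (Baseline) gives two different kinds of rule in one section:

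- Safety: "For safety evaluations, the last available assessment on or before the date of start of study treatment is taken as" baseline. The condition is a calendar date.
- Biomarkers: "the last available data collected before the first dose of study treatment will be defined as" baseline. The condition is the dose.

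Where several measurements qualify and nothing shows their order, a central laboratory value takes precedence over a local one. Among values from the same source, "then the worst value should be considered as baseline". SAP 2.7.3 repeats this for laboratory data.

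SAP 2.1.3.10 then gives two starting points for what is on treatment:

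- The observation period used for adverse events runs "from date of first administration of study treatment to 130 days" after the last. Protocol 12.5.2 agrees: "On-treatment period: from day of first dose of study medication to 130 days after last dose of study medication".
- An on-treatment assessment is one made "from date of first administration of study treatment +1 up to 130 days after the date of last administration of study treatment".

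SAP 2.7.4.2 summarises vital signs collected on treatment. SAP Table 2-4 makes the blood-pressure criteria depend on change from baseline. The shift tables in SAP 2.7.3 compare baseline with the worst on-treatment value. SAP 2.9 splits anti-drug antibody results into prevalence at baseline and incidence on treatment.

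**The concern.** A measurement taken an hour after the first injection or infusion carries the same date as the dose. Under the safety rule it qualifies as baseline and, being later than the pre-dose value, is preferred to it. Under the assessment rule it cannot be on treatment, because that window opens a day later. An adverse event starting at the same moment is treatment-emergent.

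The values exposed to this are those prompted by an acute reaction. The protocol foresees them. After an anaphylactoid reaction to an injection, "two more canakinumab IG samples (at the time of the event and 8 weeks later) need to be taken" (Protocol 8.5.1.1). Protocol 8.4.1 allows extra laboratory time points at the investigator's judgement and sends the unscheduled results to the eCRF. In the combination arm both drugs are first given on Day 1, 30 minutes apart (Protocol 6.7.2).

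Two things are at stake. The Day 1 value can drop out of tables built to show abnormal measurements. An abnormal reference value also distorts every later change from baseline for that subject and parameter.

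**Working it through.** The plan states no figure to reproduce, so the check applies its written rules to assumed records. All blood pressures below are illustrative and do not come from the documents.

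**Rules used**

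| Item | As written | By time of dose |
|---|---|---|
| Baseline | last value with date ≤ first-dose date (SAP 2.1.3.9) | last value before first dose |
| On-treatment assessment | date ≥ first-dose date + 1 (SAP 2.1.3.10) | any value after first dose |
| Notable low systolic pressure | ≤90 mmHg and fall from baseline ≥20 (SAP Table 2-4) | same |

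**Record A.** Systolic pressure: Day -5, 132; Day 1 pre-dose, 130; Day 1 at 0.5 h after dose, 84; Day 1 at 2 h, 88; Day 22, 128.

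- As written, order known: baseline is 88. The only on-treatment value is 128, a change of 128 − 88 = +40. Nothing is notable. The Day 1 values 130 and 84 are neither baseline nor on treatment.
- As written, order unknown: baseline is the worst Day 1 value, taken here as the lowest, 84. The Day 22 change is 128 − 84 = +44. Nothing is notable.
- By time of dose: baseline is 130. The falls are 130 − 84 = 46 and 130 − 88 = 42, both with values ≤90, so the criterion is met. The Day 22 change is 128 − 130 = −2.

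**Record B.** Pre-dose 120; post-dose Day 1, 84; post-dose Cycle 2 Day 1, 88.

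- Against 120: falls of 120 − 84 = 36 and 120 − 88 = 32, both notable.
- As written: 84 becomes baseline, and the second value is a change of 88 − 84 = +4. Neither is notable, although the second was measured well inside the on-treatment window.

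**No tie is needed for laboratory or immunogenicity values.** Protocol 8.4.1 lets laboratory tests done up to 3 days before first dose serve as the Cycle 1 Day 1 tests. The footnote to Protocol Table 8-5 lets the pre-dose canakinumab immunogenicity sample be drawn within the 24 hours before dosing. The planned pre-dose value may therefore be dated before Day 1. An event-triggered Day 1 value is then the only one on that date and is plainly the last that qualifies, so it becomes baseline.

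**Is there a cure elsewhere?** No other section of either document adds a pre-dose condition for safety baseline. The biomarker sentence shows that such a condition was written where it was wanted.

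**Size.** The reaction rate is an assumption. At 1%, 44 × 0.01 = 0.44 subjects per planned canakinumab-containing arm; at 5%, 44 × 0.05 = 2.2. These counts also assume that each reaction leaves a vital-sign or laboratory value in the database, so they lean high.

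**The case against.** The strongest reply is that little is lost. Day 1 adverse events are treatment-emergent in both documents, and the adverse events of special interest are built from coded event terms (SAP 2.7.1.1), not from vital signs or shifts. Clinically significant abnormal test results are themselves adverse events (Protocol 10.1.1). All safety data are listed, as are all grade 3 or 4 laboratory toxicities. This stands, and it limits the harm to derived tables.

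Scheduled Day 1 data are also largely safe. ECG, immunogenicity and pharmacodynamic assessments at Cycle 1 Day 1 are pre-dose, biomarkers have their own rule, and ECGs are only listed (SAP 2.7.4.1). The vital-sign and laboratory rows of Protocol Table 8-2 are not legible in the text reviewed, so planned post-dose vital signs cannot be shown. Nor was any statement found that unscheduled vital signs reach the database, which both illustrative records need. The exposure is essentially to unscheduled values.

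Three stronger readings are tempting, and the documents do not support them:

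- That every Day 1 assessment becomes a baseline value. Only one value per parameter does; other Day 1 values fall out of both groups, as in Record A.
- That an unordered pair always yields the reaction value. Central beats local first, and Protocol 8.4.1 makes scheduled tests central and urgent ones typically local, so the scheduled value would often survive. Immunogenicity samples carry exact times and separate unscheduled numbers, so the tie rule should not reach them.
- That Day 1 values are barred from every safety summary. SAP 2.1.3.10 also says summaries draw on the on-treatment period, which includes Day 1. The text supports two readings one day apart. Choosing the wider one would restore the value to the window but would leave the baseline error in place.

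**Conclusion.** The point holds in a limited form. The safety baseline rule lacks the pre-dose condition that the biomarker rule has, and the two on-treatment definitions in SAP 2.1.3.10 differ by a day without being reconciled for assessments. Together they can give a subject with an acute first-dose reaction a wrong reference value and can keep that value out of the notable vital-sign and laboratory shift tables. The immunogenicity consequence, a Day 1 event sample displacing the pre-dose one as baseline, follows from the same wording if these samples are treated as safety evaluations, as Protocol 12.5.2.3 does; it is the weaker part.

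A reader might infer that acute reactions vanish from the safety report. They do not, because the event tables and listings keep them. The primary and other efficacy results are untouched. The number affected is probably small and rests on an assumed rate. This is a cheap correction that should be made, not a threat to the trial's conclusions.

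**What to change.** Change two places in the SAP.

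- In 2.1.3.9: *Safety baseline is the last assessment before the first dose of study treatment by date and time. Where no clock time exists, scheduled Cycle 1 Day 1 assessments are taken as pre-dose, and unscheduled or event-triggered Day 1 assessments as post-dose.* Keep the central-over-local and worst-value rules only for ties among values already classed as pre-dose, and align SAP 2.7.3.
- In 2.1.3.10: start on-treatment assessments immediately after the first dose, so that they match the on-treatment period.

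The cost is a short text change and a small derivation change, with no new data collection. Protocol 6.6.1 already captures "The date and time of all study treatment administrations during the study" in the drug accountability log, and Protocol 8.5.1.1 puts exact dosing and sampling times on the eCRF for the pharmacokinetic, immunogenicity and pharmacodynamic samples. No section found requires clock times for vital signs or laboratory tests, so some Day 1 values will rest on the default classification, and a few may be misclassified. A listing of the Day 1 values classified by default would make that visible.
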